#### **8.2.3.1.2. Analysis of serious infections**

There are the following 3 definitions for patients with serious infections, and the analysis will be performed for each of them. As the primary evaluation, patients with serious infections during treatment period + 28 days will be used. For other definitions, the incidence of serious infections will be calculated, and other relevant analyses will be performed if such result is remarkably different from the data on treatment period + 28 days.

- Patients with serious infections during treatment period +28 days: Patients with onset of serious infections during the treatment period (+28 days): Treatment period will cover 28 days following the completion of treatment; that is, patients to be included in the analysis will be those with onset of serious infections developed from the date of the initiation of treatment + 28 days.
- Patients with serious infections during treatment period: patients with serious infections during treatment period are patients in whom serious infections developed from the date of the initiation of treatment to 1-year later (Day 366) or the date of the completion of treatment, whichever comes first.
- Patients with serious infections during overall observation period (up to 1 year): patients with serious infections during overall observation period (up to 1 year) are patients in whom serious infections developed from the date of the initiation of treatment to the date of the completion or discontinuation of follow-up.

Other definitions used in the comparison of serious infections are shown in Table 6.

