##### [11] Laboratory tests (peripheral leukocyte count, peripheral lymphocyte count, $\beta$ -D-glucan)

2) Survey form

(1) Patient characteristics prior to and at the start of treatment

The following will be recorded for both treatment groups.

[1] Height/weight

[2] Inpatient/outpatient status

Indication (Patients with rheumatoid arthritis), stage and grade (Steinbrocker stage), and functional class (Steinbrocker functional class)

[3] Duration of disease

[4] Clinical history (past history and concurrent illness)

[5] History of smoking (history of smoking at treatment start)

[6] Family history of malignant tumor

(2) Previous treatment drugs for rheumatoid arthritis (3 months before treatment start)

The following will be recorded for both treatment groups.

[1] MTX

- Past use (presence/absence)
- Weekly dosage
- Duration of treatment

[2] Oral steroid use for rheumatoid arthritis

- Past use (presence/absence), period or treatment

[3] Tacrolimus

- Past use (presence/absence)
- Duration of treatment

(3) Dose record

[1] Xeljanz group

Number of doses per day, treatment period, reason for change (if there has been a change in administration)

[2] Control group

If there has been a switch to another type of pharmacotherapy, excluding Xeljanz, during the observation period, the case will be handled as a continued surveillance case, and the treatment record should be continuously entered.

In cases where Xeljanz has been administered, surveillance as a member of the control group will be handled as discontinued, and registration in the Xeljanz group will be necessary.

● MTX

Name of drug (name of product), weekly dosage, and duration of treatment

● Pharmacotherapy with drugs other than MTX (biological preparation, DMARDs, immunosuppressants, oral steroid preparations)

Name of drug (name of product), daily dosage (oral steroids), and duration of treatment

(4) Concomitant therapy (Xeljanz group)

For drug therapy, covering the period starting 3 months prior to the start of treatment in this Surveillance

and ending at the completion or discontinuation of the observation period will be completed. Medications used for the treatment of adverse events should also be recorded.

[Concomitant therapies coadministered with Xeljanz]

- [1] MTX
- [2] Biological preparations\*
- [3] DMARDs other than MTX and immunosuppressants\*
- [4] Oral steroid
- [5] Other drugs

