### 7.3 End-of-surveillance (discontinuation) record

Confirm whether or not treatment can be continued by Xeljanz or control group at end of observation period. If treatment by Xeljanz group or control group cannot be continued, write date of discontinuation and select item that corresponds to reason (multiple responses possible).

However, even if a switch to another type of pharmacotherapy, excluding Xeljanz, has been made in the control group after registration is complete, it will be handled as a continuing surveillance case, and if the pharmacotherapy has been discontinued, it will be handled as a surveillance discontinued case.

If adverse event or death is selected as the reason, the details thereof should be recorded in the adverse event section. [Also, for the control group, if the reason selected is associated with malignant tumor and death of patient (treatment start to 36 months) or serious infection (treatment start to Month 12 of treatment), the details thereof should be recorded].

 
[1] Remission
 
[2] Inadequate clinical response
 
[3] Adverse event
 
	} [1]-[3]: Subject to follow-up survey e)

 
[4] Death (date of death)
 
[5] No revisit
 
[6] Transfer to another hospital/department (name of hospital/department)
 
[7] Treatment with Xeljanz tablets (*Only applicable for the survey form for the control group)
 
	} [4]-[7]: End surveillance if any of the following apply

 
[8] Other
 
	

e) However, the observation period for subjects who correspond to "1) Xeljanz group (2) in 6.5 Observation period" will be only 6 months after the date of treatment start (Booklet 1) and no follow-up surveillance will be conducted.

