**Table 6. Definitions in the Comparison of Serious Infections**

Term	Definition
Patients without serious infections	Patients who do not correspond to the each definition of patients with serious infections
Time to serious infections during the treatment period (+28 days)	Date of the development of serious infections- date of the initiation of treatment + 1 Both treatment groups will be analyzed for the duration of treatment + 28 days (up to not longer than 1 years).
Censoring period for patients without serious infections during the treatment period (+28 days)	Date of the completion of treatment + 28- date of the initiation of treatment + 1 Both treatment groups will be analyzed for the duration of treatment + 28 days (up to not longer than 1 years).
Time to serious infection during treatment period	Date of the development of serious infection - date of the initiation of treatment + 1 The upper limit is 1 year (366)
Censoring period for patients without serious infections during treatment period	Date of the completion of treatment - date of the initiation of treatment + 1 The upper limit is 1 year (366)
Time to serious infection during overall observation period	Date of the development of serious infection - date of the initiation of treatment + 1 The upper limit is 1 year (366)
Censoring period for patients without serious infections during overall observation period	Date of completion or discontinuation of follow-up - date of the initiation of treatment + 1 The upper limit is 1 year (366)

- **Development of serious infections**

The number of serious infections in each group and the proportion of occurrence are calculated for each SOC and PT. Furthermore, it is calculated for each infection type.

- **Incidence rate of serious infections**

The number of patients with serious infections in each group, incidence rate, and the 95% confidence interval will be calculated in accordance with [Section 8.1.5](#).

In addition, the incidence ratio between treatment groups and the 95% confidence interval and the difference in incidence rate between treatment groups and the 95% confidence interval will be calculated.

The above analyses will be also conducted for serious infections excluding serious herpes zoster and for serious herpes zoster, respectively.

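### The primary serious-infection window appears to release Xeljanz patients 28 days after Xeljanz ends but to keep controls who switch to another non-Xeljanz drug, and the SAP does not define when control treatment ends

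*SAP*

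**What the plan says.** SAP 8.2.3.1.2 defines three windows for serious infection and chooses one: "As the primary evaluation, patients with serious infections during treatment period + 28 days will be used". Table 6 gives the censoring time for that window as "Date of the completion of treatment + 28- date of the initiation of treatment + 1" and applies it to both groups: "Both treatment groups will be analyzed for the duration of treatment + 28 days (up to not longer than 1 years"). Neither place says what completion of treatment means for a control who takes several drugs in turn.

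The protocol says how a change of drug is handled in controls. In Protocol 7.1, survey form item (3) (dose record), for a switch to anything other than Xeljanz, "the case will be handled as a continued surveillance case, and the treatment record should be continuously entered". Protocol 7.3 repeats the rule: "even if a switch to another type of pharmacotherapy, excluding Xeljanz, has been made in the control group", "it will be handled as a continuing surveillance case". Two events end control surveillance. One is a move to Xeljanz: "In cases where Xeljanz has been administered, surveillance as a member of the control group will be handled as discontinued". The other is stopping drug therapy: "if the pharmacotherapy has been discontinued, it will be handled as a surveillance discontinued case".

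For the other two windows, including overall observation up to 1 year, SAP 8.2.3.1.2 guarantees an incidence. Further analyses follow only if the result looks markedly different from the primary one, and no threshold is given.

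**The concern.** The wording of the window is the same in both groups, but the exposure it tracks is probably not. A Xeljanz patient who responds poorly and changes drug leaves the primary analysis 28 days later. A control who responds poorly and changes to another non-Xeljanz drug appears to remain. Control person-time would then include later-line time that is removed from the Xeljanz group.

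If infection risk differs after failure or switching, the comparison mixes the drug effect with this difference in follow-up. The planned Cox and IPTW analyses use the SAP 6.3 covariates, which are essentially patient background at or before the start. They do not address exit from follow-up that depends on what happens after the start. Serious infection is one of the two comparisons named in the protocol objective. With higher risk after failure, the error makes Xeljanz look safer.

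**Working it through.** **Step 1. When does control treatment end?** The SAP has no definition, so the reading is built from several places.

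- Protocol 7.1 and 7.3: a switch to another non-Xeljanz drug continues both the case and the treatment record.
- SAP 8.2.1: discontinuation is timed to the end of Xeljanz in one group and to the end of the survey in the other.
- SAP Table 2: inadequate effect and adverse events are discontinuation reasons for the Xeljanz group only.
- SAP Appendix 11.1.1: Day 1 for controls is the earliest start of any recorded drug.
- SAP 8.2.2: duration of administration runs from the oldest start to the newest end date. The formula is introduced for the Xeljanz group, but Table 4 does not restrict this item to it.
- SAP 5.1.2: MTX counts as a control drug. On this reading a control who stops a biologic but stays on MTX has not finished treatment, while a Xeljanz patient who stops Xeljanz but stays on MTX has.

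Together these point to the whole sequence of non-Xeljanz drugs, but this is an inference.

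**Step 2. The plan's own figure.** No serious-infection rate or switching rate is given. The only event count is 104 malignant tumors in 4000 Xeljanz patients (Protocol 3). With dropout linear to 50% at 3 years, mean follow-up is 3 × (1 + 0.5)/2 = 2.25 years, and 4000 × 2.25 × 0.0116 = 104.4, which reproduces it. Linear dropout implies 50%/3 = 16.7% in year 1; exponential dropout would imply 1 − 2^(−1/3) = 20.6%. I use these only as a stand-in for stopping the initial treatment.

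**Step 3. Size of the effect.** Assumptions: no true difference between the drugs; the same share q stops in both groups, uniformly over the year; all are otherwise observed for the full year; controls who stop move to another non-Xeljanz drug; and the infection rate after failure is k times the earlier rate in both groups.

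- 28 days as a fraction of a year: L = 28/365.25 = 0.0767
- Post-failure time: P = q/2
- Time removed from the Xeljanz group: R = q(1 − L)²/2 = 0.4263q
- Xeljanz rate: [(1 − P) + k(P − R)]/(1 − R)
- Control rate: (1 − P) + kP

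For q = 1/6 and k = 2: P = 0.08333, R = 0.07105 and P − R = 0.01229. The Xeljanz rate is (0.91667 + 2 × 0.01229)/0.92895 = 1.0132. The control rate is 0.91667 + 2 × 0.08333 = 1.0833. The ratio is 0.935.

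| q | R | k = 1 | k = 1.5 | k = 2 | k = 3 |
|---|---|---|---|---|---|
| 16.7% | 7.1% | 1.00 | 0.966 | 0.935 | 0.880 |
| 20.6% | 8.8% | 1.00 | 0.959 | 0.922 | 0.857 |
| 30% | 12.8% | 1.00 | 0.942 | 0.892 | 0.808 |
| 50% | 21.3% | 1.00 | 0.910 | 0.837 | 0.729 |

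If risk falls after failure, the sign reverses. With k = 0.5 and q = 1/6 the Xeljanz rate is (0.91667 + 0.5 × 0.01229)/0.92895 = 0.9934, the control rate is 0.91667 + 0.5 × 0.08333 = 0.9583, and the ratio is 1.04.

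**The case against.** **The asymmetry is inferred.** Table 6 states one rule for both groups, and the protocol passages govern whether surveillance continues, not when treatment is complete for analysis. This stands. What can be shown directly is an undefined term; the passages in Step 1 make the asymmetric reading the likely one, not a certain one.

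**A reader might infer that controls are followed through every change of drug and that only the Xeljanz group is cut.** The protocol does not support that. Controls who start Xeljanz, or who stop drug therapy altogether, are also discontinued.

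**A reader might take the overall observation period as a fully symmetric benchmark.** It is not. Protocol 7.3 lists treatment with Xeljanz among the reasons that end surveillance, and this applies to controls only. Xeljanz patients who stop for inadequate response or an adverse event are followed up under Protocol 7.3 and 7.7. SAP 6.1.1 adds that events learned of after transfer to a non-contracted facility can enter the database for the Xeljanz group only. This window also counts infections on later drugs as Xeljanz-group events. It is a useful companion with different weaknesses.

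**A reader might expect a bias of 11 to 20%.** That follows from putting 25% of first-year control time after a switch and leaving no post-failure time in the Xeljanz group: 1/(0.75 + 0.25 × 1.5) = 0.89 and 1/(0.75 + 0.25 × 2) = 0.80. With uniform switch times it needs about half of controls to switch within a year, and it ignores the 28-day tail. The documents give no basis for that share.

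**Part of the remedy may already exist.** The SAP revision table (version 8.0) places a sensitivity analysis of the group comparison in 8.2.3.1.4, which appears to fall in redacted text. A version censored at switch therefore cannot be called absent.

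**The existing outputs cover something.** An incidence is guaranteed for every window, and it may be meant to include the ratio and difference. The adjusted and weighted hazard ratios are clearly conditional. SAP 4 also describes all testing as exploratory, which limits the stakes but does not remove a bias from the estimate.

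**Conclusion.** The concern holds in a limited form. The control end-of-treatment date is undefined. The most natural reading keeps controls in the primary analysis through switches among non-Xeljanz drugs, while Xeljanz patients leave 28 days after Xeljanz ends.

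If infection risk after failure is 1.5 to 2 times the earlier risk, the ratio is about 3 to 6% too favourable to Xeljanz at 17% stopping within a year, and 9 to 16% at 50%. There is no bias if risk is unchanged. The stopping share and the risk multiplier are assumptions; the 17% borrows the plan's 3-year dropout figure as a proxy. The bias is modest at that anchor, but nothing in the visible plan guarantees an adjusted result that would reveal it.

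**What to change.** 1. In SAP 8.2.3.1.2 and Table 6, state the date on which treatment is complete for a control, covering switches between non-Xeljanz drugs and stopping one drug while MTX continues. In the same edit, correct the time-to-serious-infection item, which sends censoring to Table 5 (malignant tumors, no 1-year cap) instead of Table 6.
2. Remove the condition on the overall observation period (up to 1 year). Always report the rate ratio, the adjusted hazard ratio and the IPTW hazard ratio there. State its remaining asymmetries: controls who start Xeljanz are cut, and post-transfer information is collected only for Xeljanz. Because of the second, also report the version based only on CRF information, which SAP 6.1.1 already provides for.
3. Unless the redacted sensitivity section already contains it, add a version that censors controls 28 days after they stop their initial drug(s). The dose record holds drug names and durations, SAP Table 4 already identifies the initial drugs, and SAP 8.2.2 already tabulates how many controls remain on them. That tabulation would also replace the assumed stopping share with data.

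The primary definition need not change and no new data are required. The cost is a SAP clarification and extra programming.

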**Table 6. Definitions in the Comparison of Serious Infections**

Term	Definition
Patients without serious infections	Patients who do not correspond to the each definition of patients with serious infections
Time to serious infections during the treatment period (+28 days)	Date of the development of serious infections- date of the initiation of treatment + 1 Both treatment groups will be analyzed for the duration of treatment + 28 days (up to not longer than 1 years).
Censoring period for patients without serious infections during the treatment period (+28 days)	Date of the completion of treatment + 28- date of the initiation of treatment + 1 Both treatment groups will be analyzed for the duration of treatment + 28 days (up to not longer than 1 years).
Time to serious infection during treatment period	Date of the development of serious infection - date of the initiation of treatment + 1 The upper limit is 1 year (366)
Censoring period for patients without serious infections during treatment period	Date of the completion of treatment - date of the initiation of treatment + 1 The upper limit is 1 year (366)
Time to serious infection during overall observation period	Date of the development of serious infection - date of the initiation of treatment + 1 The upper limit is 1 year (366)
Censoring period for patients without serious infections during overall observation period	Date of completion or discontinuation of follow-up - date of the initiation of treatment + 1 The upper limit is 1 year (366)

- **Development of serious infections**

The number of serious infections in each group and the proportion of occurrence are calculated for each SOC and PT. Furthermore, it is calculated for each infection type.

- **Incidence rate of serious infections**

The number of patients with serious infections in each group, incidence rate, and the 95% confidence interval will be calculated in accordance with [Section 8.1.5](#).

In addition, the incidence ratio between treatment groups and the 95% confidence interval and the difference in incidence rate between treatment groups and the 95% confidence interval will be calculated.

The above analyses will be also conducted for serious infections excluding serious herpes zoster and for serious herpes zoster, respectively.

For covariates concerning serious infections ([Section 6.3](#)), incidence by single factor will be calculated, and the pooled incidence ratio and the 95% confidence interval and the pooled difference in incidence rate and the 95% confidence interval will be calculated.

Incidence ratio with its 95% CI will be calculated for events of herpes zoster, opportunistic infection, and tuberculosis as well as “serious infections” .

- **Incidence proportion of serious infections**

The number of patients with serious infections in each group, the incidence proportion, and the 95% confidence interval will be calculated in accordance with [Section 8.1.5](#).

In addition, the ratio of incidence proportion and the 95% confidence interval and the difference in incidence proportion and the 95% confidence interval will be calculated.

The above analyses will be also conducted for serious infections excluding serious herpes zoster and for serious herpes zoster, respectively.

For covariates concerning serious infections ([Section 6.3](#)), the incidence proportion by single factor will be calculated, and the ratio of the pooled incidence proportion and the 95% confidence interval and the difference in the pooled incidence proportion and the 95% confidence interval will be calculated. Age will be handled as categorical data.

Incidence proportion with its 95% CI will be calculated for events of herpes zoster, opportunistic infection, and tuberculosis as well as “serious infections” .

- **Analysis of time to serious infection**

- Time to serious infection in each group will be summarized in accordance with [Section 8.1.4](#). As for the censoring period in patients without serious infection, [Table 5](#) will be followed. In addition, a graph showing the transition of the incidence rate estimated using the calculated parameters by applying the Weibull distribution together with the Kaplan-Meier plot, and a graph of the transition of the hazard function are created. **Adjusted hazard ratio for the development of serious infections**

As for time to serious infection, the adjusted hazard ratio of the Xeljanz group to the control group for the development of serious infections and the 95% confidence interval will be calculated in accordance with [Section 8.1.5](#). Covariates used for adjustment are shown in [Section 6.3](#).

As for the development of serious infections in the Xeljanz group compared to the control group, the propensity score- weighted (inverse probability of treatment weighting, IPTW) hazard ratio and the 95% confidence interval will be calculated. The weight will be similarly obtained in [Section 8.2.3.1](#).

In addition to the propensity score-weighted, further adjustment using a model with covariates of large effect will be conducted. The covariate which show large change in adjusted hazard ratio from the non-adjusted hazard ratio in the univariate model, will be included in this model in order to control the number of covariates in the model.

- **Distribution of propensity score and covariates before and after adjustment for hazard ratio of serious infections**

The distribution of propensity scores before and after adjustment by weighting of propensity scores is estimated using kernel density estimation and shown by violin plot. In the control group, a boxplot of weights is created.

In addition, the proportion of each category of patient background used for the covariate and the difference between the standardized groups are calculated before and after adjustment. The standardized difference is treated as a continuous amount in the patient background of 3 or more categories, and calculated by the difference / standard deviation of the average value of each group. In the patient background of the binary data, it is calculated by the difference / standard deviation of the ratio of each group. In addition, parameters are calculated in logistic regression model.

